COMIRB Protocol
COLORADO MULTIPLE INSTITUTIONAL REVIEW BOARD
[name] [contact] [contact]

PROTOCOL #: 13-2639

(Use Protocol Manager on the COMIRB Website)

Version Date: December 9, 2016

Project Title: Improved behavioral outcome in allogeneic hematopoietic stem cell transplant patients by reducing caregiver distress: Behavioral and physiological evidence

Principal Investigator: [name]

**Co-Investigators: [name]
[name]
[name]**

**[name]
[name]
[name]**

I. Hypotheses and Specific Aims:

Patients receiving an allogeneic hematopoietic stem cell transplant (HSCT) undergo a demanding conditioning protocol. In contrast to cancer treatments using standard-dose chemotherapy, radiation, and/or surgery, treatment protocols for HSCT are more intense and life threatening. Following transplantation, patients are at increased risk for graft versus host disease (GvHD). To ensure adequate support, monitoring and safety, allogeneic HSCT patients are required to have a caregiver available 24/7 for at least the first 100 days following transplantation and occasionally longer if complications arise. Allogeneic caregivers assist with a complicated medical procedure with 70% patient survival. The patient's quality of life (QOL) is dependent on the quality of care provided by their caregiver. Caregiver distress impacts the quality of care they provide and thus patient QOL.

We showed that a behavioral intervention for caregivers of allogeneic HSCT patients reduced caregiver distress. *A gap remains with regard to evaluating intervention impact on patient QOL.* During the first 100 days, patients may be poor targets for behavioral intervention due to significant fatigue and debilitation. Carry over to patients as improved care may derive from caregivers participating in supportive programs. Patient and caregiver dyads will be randomized to either treatment as usual (TAU) or "fone" PsychoEducation and Relaxation (fPER) which provides a combination of face to face sessions and Smartphone video chat when a caregiver is unable access the clinic to meet with an interventionist. fPER caregivers will receive a biofeedback device for stress management. 225 dyads will be randomized from 2 sites (private and university based) and followed for 6 mo. following transplantation. Specific aims are:

Hypotheses:

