A possible problem rests in the burden for the caregiver. We have worked hard to minimize the inconvenience to the caregiver in this project to reduce drop outs and maintain compliance. Another issue is related to patient death or subject dropout. For this reason, we use intent to treat design with the last valid measure carried forward. Subject dropouts will be considered to occur completely at random unless otherwise indicated. Caregivers are expected to be generally healthy. It is appreciated that caregiver medications might impact biomarkers. Thus medication use will be treated as a covariate in the analysis. We appreciate that eliminating subjects with illnesses requiring medications would skew the caregivers to only the very healthy and least likely to have health impairments associated with caregiving. Such a strategy would distort the potential impact of the intervention on biomarkers and behavior and weaken implications for caregivers in general. It is possible that objective caregiver burden might not change as a function of treatment since in many respects the time factors and financial burden do not change regardless of the intervention. However it is expected that the subject's perception of how stressful they present themselves (subjective burden) will change and this will be seen in affect and stress measures. In summary we remain very excited about this study as it will provide empirical evidence regarding the efficacy of the fPER intervention for caregivers of BMT patients. Further, it will provide behavioral and biomarker corroboration regarding the efficacy of fPER.

Data Safety And Monitoring Plan

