Data Aggregation, Distributional Assumptions, Missing Data/Attrition. Data will be screened for errors and outliers. Appropriate transformations will be made for non-normal outcomes. The pattern of participant dropout will be examined to ensure a reasonably equal distribution of participants lost to follow-up between groups. The analytic approach proposed uses maximum likelihood techniques that can include participants with incomplete data without need for imputation. These techniques are robust under certain conditions such that group comparisons will not be biased as long as missing data is ignorable.^{132,133} If this is not sufficient to minimize influences of particular observations, a sensitivity analysis will be conducted to help determine effects of missing data. Separate analyses of only those participants who complete the study will be conducted.

Verification of Randomization and Inclusion of Covariates. Preliminary analyses will validate that there are no baseline differences between intervention groups. We expect baseline differences will be accounted for by randomization, but should differences remain we will co-vary variables that are both correlated with the outcome and that differ by group.

Analytic Strategy In general, outcomes will be analyzed with linear mixed models comparing intervention (**fPER**, TAU) in patients and caregivers separately. An alpha level of 0.05 will be used to evaluate significance of the a priori planned comparisons. Two-tailed tests are proposed in order to detect differences between **fPER** and TAU in either direction. The software SAS PROC MIXED will be used.¹³⁴ The analytic aims and hypotheses are briefly stated, followed by overall analytic plan for primary and secondary outcomes:

Aim 2: Assess patient QOL following an allogeneic HSCT by the FACT-BMT as the primary patient outcome. Patients whose caregivers receive fPER will have improvements in FACT-BMT compared to TAU.

Aim 3: Test impact of fPER on caregiver composite distress score of depression, anxiety, and stress as the primary caregiver outcome. Caregivers who receive fPER will have reduced distress compared to TAU.

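### Carry-forward is prescribed for patient death as well as dropout, which assigns FACT-BMT scores after death and contradicts the likelihood analysis without imputation

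*Combined protocol and SAP*

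**What the plan says.** Section IV.E (Potential Scientific Problems) treats death and dropout as one issue with one remedy: "patient death or subject dropout. For this reason, we use intent to treat design with the last valid measure carried forward". Its next sentence adds: "Subject dropouts will be considered to occur completely at random unless otherwise indicated".

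Section IV.F (Data Analysis Plan), in the paragraph on missing data and attrition, describes a different method: "maximum likelihood techniques that can include participants with incomplete data without need for imputation". It says that "group comparisons will not be biased as long as missing data is ignorable". If that is not enough, "a sensitivity analysis will be conducted to help determine effects of missing data"; no method is given and death is not mentioned. It also states: "Separate analyses of only those participants who complete the study will be conducted".

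The primary patient model in IV.F is a linear mixed model of FACT-BMT at four times (pre-transplant, 6 weeks, 3 months, 6 months), with a random subject effect and no survival component. Section I describes the setting: "Allogeneic caregivers assist with a complicated medical procedure with 70% patient survival". No time point is attached to that figure. The patient procedures table in IV.C schedules a chart review at month 6.

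**The concern.** A score due after death is not a missing value. It does not exist. Carry-forward supplies one anyway. Section IV.D (FACT-BMT) says that quality of life falls during hospitalization and may stay low for up to a year, so a score carried from before transplant may be higher than anything the patient would have reported later.

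The likelihood model in IV.F supplies no explicit value. By treating post-death scores as ignorable missing data, however, it estimates a month-6 mean as if those patients still had scores. Section IV.F neither says this nor defines another target.

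An analyst following IV.E and one following IV.F would therefore produce different primary FACT-BMT results from the same data. A reader of either could not say to which patients the contrast applies. FACT-BMT is the primary patient outcome and deaths are to be expected in this setting, so the gap affects the main result.

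**Working it through.** **1. The two rules side by side, for a patient who dies between week 6 and month 3**

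| | IV.E | IV.F |
|---|---|---|
| 3- and 6-month FACT-BMT | week-6 score entered | nothing entered; treated as ignorably missing |
| Implied month-6 mean | includes a score from before death | as if the patient still had a score |
| Meaning for those who die | not stated | not stated |

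Both cannot govern the primary analysis.

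**2. Where deaths sit in the plan's own numbers**

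The sample size text in IV.F assumes losses of 34% at 3 months and 45% at 6 months, based on the prior caregiver trial. These reproduce the lower rows of its effect-size table: 112 × (1 - 0.34) = 73.9, shown as 74; 112 × (1 - 0.45) = 61.6, shown as 62. Deaths are not separated from other losses, so 6-month mortality cannot be recovered.

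**3. How many patients could be affected**

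Mortality is an assumption; N = 225 is from the protocol.

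- 10%: 0.10 × 225 = 22.5, about 23
- 20%: 0.20 × 225 = 45
- Ceiling, only if the 70% survival applied at 6 months: 0.30 × 225 = 67.5, about 68

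**4. Bias with no true effect (simulation)**

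Assumptions: random-intercept variance 0.6; residual variance 0.4; log-odds of death -1 per unit of latent quality of life; mean trajectory 0, -0.6, -0.3, -0.1 SD at the four visits; death equally likely in each interval between visits. Entries are the month-6 difference in SD, higher- minus lower-mortality arm.

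| Mortality | Survivors only | Carry-forward | Mixed model* |
|---|---|---|---|
| 30% v 20% | 0.05 | -0.02 | 0.01 |
| 30% v 15% | 0.08 | -0.03 | 0.02 |
| 20% v 20% | about 0 | about 0 | about 0 |

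*Relative to the hypothetical mean with no deaths, which is itself the quantity in question.

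Across other assumed trajectories, and mortality from 15% v 10% to 30% v 15%, carry-forward bias ran from about -0.05 to +0.03 SD. The sign depends on whether carried scores are, on balance, better or worse than the month-6 scores they stand in for.

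**5. A cruder bound**

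Hold the survivors' mean equal in both arms. The bias is then (difference in mortality) × (carried score minus survivors' mean). With a 5-point difference and a 0.5 SD gap it is 0.05 × 0.5 = 0.025 SD; with 10 points and 1 SD it is 0.10 × 1 = 0.10 SD, in either direction. This ignores the offsetting selection among survivors that the simulation includes.

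**6. If there is a true effect**

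If carried scores show none of the effect, carry-forward multiplies the survivors' effect by (1 - mortality): 0.90 at 10% and 0.80 at 20%, even with equal mortality. That is an extreme case, since scores from week 6 or month 3 may already reflect some benefit.

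**The case against.** The strongest reply is that IV.F is the analysis plan and already governs. Its mixed model imputes nothing, so the carry-forward sentence in IV.E is a stray remark. The plan also examines dropout by group, allows a sensitivity analysis, adds a completers analysis, schedules a month-6 chart review and has the monitoring board review the status of all subjects. Nothing projects a survival effect of a caregiver programme, and equal mortality with no true effect gives about zero bias.

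Much of this stands. The bias is small, and these elements are partial mitigation. But none of them is specified for death, completers are a post-randomization subset, and no text says that IV.F overrides IV.E. The contradiction reaches all missing data, not only death; that widens the need to reconcile the sections.

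Four stronger readings are tempting and are not supported:

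- *Deaths are assumed completely at random.* That sentence concerns subject dropouts and is qualified. IV.E lists death and dropout as two things, though it gives them one remedy.
- *30% of patients will die during follow-up.* The 70% survival figure has no time point.
- *The planned primary analysis is biased by 0.06-0.08 SD.* Values of that size belong to a comparison of survivors or completers under unequal mortality. Neither documented primary method is that comparison.
- *Calling the contrast while-alive resolves the matter.* The label does not change what the mixed model estimates.

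**Conclusion.** The concern holds in this form: IV.E prescribes a rule that creates FACT-BMT scores after death, IV.F prescribes a method that conflicts with it, and neither defines the primary contrast for patients who die. This part rests on the text alone.

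The numerical stakes are modest and depend on assumptions. At an assumed 6-month mortality of 10-20%, about one in ten to one in five patients would be affected. Simulated carry-forward bias stays within about 0.05 SD in either direction, needs unequal mortality, and has a sign that cannot be known in advance because the quality-of-life trajectory and the link between death and quality of life are assumed. The change should be made because the primary estimate is undefined for these patients and the correction is cheap, not because a large bias has been shown.

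**What to change.** 1. Delete carry-forward from IV.E, so that the IV.F mixed model on observed scores governs, and state that no FACT-BMT value is carried forward or imputed after death.
2. Record death separately from dropout, and report deaths by arm beside the FACT-BMT result, using the month-6 chart review already scheduled.
3. State plainly in IV.F that the mixed model treats post-death scores as ignorable missing data, so its month-6 contrast is not a while-alive effect.
4. Prespecify one month-6 sensitivity analysis that ranks death below every observed FACT-BMT score and compares the arms on ranks. Say in advance how living patients without a month-6 score enter it.

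Cost: wording in two sections, one recorded item from a review already planned, and one extra analysis. The drawback of the rank analysis is that it mixes survival with quality of life, so it should stay secondary.

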Allogeneic hematopoietic stem cell transplant (HSCT) caregivers must be available 24/7 for the first 100 days and often longer following a transplant. However behaviorally and more importantly medically healthy caregivers are essential for the best patient outcome. Few interventions for caregivers have been tested by randomized clinical trials (RCT). Our objective is to determine if a stress management intervention for allogeneic HSCT caregivers compared to self-care relying on resources of the transplant program (treatment as usual, TAU) would be associated with lower stress. We designed a randomized control trial with intent-to-treat of an eight session manualized stress management intervention provided to caregivers following transplant. Subjective behavioral data collected longitudinally for 12 months using standardized instruments was entered blindly. The HSCT caregivers were recruited from a community transplant program between November 2008 and April 2012. The study included a consecutively approached sample of 267 caregivers of allogeneic HSCT patients. 148 (mean age=53.5 years, 75.7% female) were randomized to a manualized intervention (n=74) or TAU (n=74). 101 caregivers reached the three month follow-up with drop outs associated with patient and/or caregiver factors. The intervention included an eight session stress management program provided to caregivers by a social worker during the immediate post-transplant period that focused on learning about stress, changing role(s) of the caregiver, cognitive behavioral approach to managing stress, paced respiration with a commercial biofeedback device, and identifying resources. A panel of questionnaires and physiological markers was collected from the caregivers five times over the course of one year beginning in the peri-transplant period. The primary outcome measure was self-reported perceived stress. Secondary outcome measures included depression, anxiety, caregiver burden, physical health, sleep, trauma and composite scores of these measures. Groups did not differ at baseline. Controlling for age, the intervention resulted in significantly lower ($p=0.039$) caregiver perceived stress (primary outcome) at 3 months post-transplant (Mean=20.0, SD=1.0) compared to TAU (Mean=23.0, SD=1.0) with an effect size (ES) of 0.39. The intervention group showed significantly better ($p=0.019$) scores on a secondary composite score that includes depression, anxiety, and other distress measures (Mean=-0.22, SD=0.13) compared to TAU (Mean=0.23, SD=0.13) with an ES of 0.45. This study had limitations due to problems with low minority subject recruitment, logistics of collecting dependent measures when patients and caregivers moved out of the area, as well as missing data. While needing further study within more settings, this approach is likely to improve caregiver well-being and potentially that of patients.

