patient QOL is indirect, and thus smaller effect sizes would be expected. We estimated minimum effect sizes detectable for different power specifications for a recruited sample size of 112 per treatment group and also for smaller sample sizes, allowing for increased variability due to estimated losses to follow-up of 34% at 3 mo., and 45% at 6 mo. based on our prior caregiver trial. Estimates are conservative since **fPER** has been specifically modified to reduce attrition. 112 dyads (consisting of a caregiver and patient) randomized to each group provide excellent power (>95%) for detecting the medium effect size expected for the composite distress score in caregivers and are necessary to provide adequate power (80-85%) for detecting smaller effect sizes expected for the FACT-BMT QOL measure in patients. Estimates are also conservative because mixed model analyses that include all subjects (even those with only a single observation) have been shown to provide the greatest power.¹²⁷

G. Summarize Knowledge to be Gained:

This study will provide empirical evidence regarding both behavioral and possible physiological efficacy of a stress management psychoeducation program for caregivers and the impact on patient QOL. This is one of the few studies of its kind that promises to provide not only information regarding behavioral outcome for the patients as far as quality of life but also impact their caregivers. The results of this study will lead to the availability of a manual developed for this intervention that can be disseminated to other HSCT programs leading to improved patient QOL and reduced caregiver distress.

H. References:

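### Carry-forward triggered by patient death (IV.E) conflicts with the no-imputation mixed model (IV.F), and neither says how a bereaved caregiver's primary distress score is obtained

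*Combined protocol and SAP*

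**What the plan says.** IV.E (Potential Scientific Problems) names as an issue "patient death or subject dropout. For this reason, we use intent to treat design with the last valid measure carried forward". It adds: "Subject dropouts will be considered to occur completely at random unless otherwise indicated". Neither sentence distinguishes the patient from the caregiver.

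IV.F (Data Analysis Plan) takes a different route. It relies on "maximum likelihood techniques that can include participants with incomplete data without need for imputation", models patients and caregivers separately, and takes as its Aim 3 endpoint the "caregiver composite distress score of depression, anxiety, and stress as the primary caregiver outcome". The primary caregiver model contains group, clinic, time, their interactions and caregiver age, with subject as a random effect. A sensitivity analysis is to be added only if the likelihood approach proves insufficient, and its content is not described. A completers analysis is also planned. The power section in IV.F argues that "mixed model analyses that include all subjects (even those with only a single observation) have been shown to provide the greatest power".

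IV.C schedules questionnaires for both members of the dyad at about 6 weeks, 3 months and 6 months after transplant. It gives no rule that ends the caregiver's assessments when the patient dies.

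On how often this may arise, Section I says: "Allogeneic caregivers assist with a complicated medical procedure with 70% patient survival". It gives no time horizon. Section III reports for the prior trial that "101 caregivers reached the three month follow-up with drop outs associated with patient and/or caregiver factors", and the power section plans for "estimated losses to follow-up of 34% at 3 mo., and 45% at 6 mo. based on our prior caregiver trial".

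**The concern.** The caregiver composite is built from self-report scales (PSS, CES-D, STAI). A caregiver whose patient has died is alive, remains in the randomised population, and can still be asked to complete them. A plan that names the patient's death as a reason for carry-forward, with no caregiver exception, can be applied so that a pre-death score stands in for an outcome that could have been collected.

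The mixed model does not settle the matter. If bereaved caregivers stop contributing, the likelihood analysis gives valid group comparisons only when the missingness is ignorable. The model has no term for bereavement, so their later distress is in effect predicted from caregivers who are still observed. The assumption of dropout completely at random also fits poorly with the prior trial, where dropout was linked to patient or caregiver factors.

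Aim 3 asks whether fPER lowers caregiver distress. As written, two analysts could follow the plan in good faith and produce different Aim 3 results, neither of which need include distress after bereavement.

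**Working it through.** **Step 1. The two rules side by side, for one caregiver.** The patient dies in week 8, and the caregiver completed the baseline and 6-week questionnaires.

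- IV.E, caregiver not assessed afterwards: the 6-week composite is used at both 3 and 6 months.
- IV.F, caregiver not assessed afterwards: 3 and 6 months are missing and treated as ignorable.
- Either section, caregiver assessed at 3 and 6 months: the observed values exist and nothing needs to be carried forward.

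If the patient dies after the 3-month visit, only the 6-month value is affected. The plan does not say which case applies.

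**Step 2. What the plan's own sample sizes imply.** The smaller rows of the power table are 74 and 62 dyads per group. These equal the planned 112 less the stated losses: 112 × (1 − 0.34) = 73.9 and 112 × (1 − 0.45) = 61.6. The power section therefore counts lost participants as missing, which fits IV.F and not carry-forward.

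**Step 3. Size of the carry-forward effect (illustration).** The plan has no figure for this and no death rate by 6 months. Inputs:

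- Effect of 0 at baseline and 0.45 SD at 3 months: from the prior trial in Section III (no baseline difference; composite effect size 0.45).
- Effect of 0.45 SD at 6 months, also in bereaved caregivers: assumption.
- Effect e6 at 6 weeks: assumption, varied over 0, 0.225 and 0.45.
- Deaths spread evenly over 26 weeks, with the 3-month visit at week 12 as in the procedure tables: assumption.
- Fraction d of patients dying by 6 months: assumption, 0.10 and 0.30. The upper value applies the 70% survival as if it were a 6-month figure.
- No other losses, and no bereaved caregiver assessed after the death: assumption.

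Deaths in weeks 0–6 carry the baseline value, those in weeks 6–12 the 6-week value, and those in weeks 12–26 the 3-month value:

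6-month estimate = (1 − d) × 0.45 + d × [(6/26) × 0 + (6/26) × e6 + (14/26) × 0.45]

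| d | Caregivers (225 × d) | e6 = 0 | e6 = 0.225 | e6 = 0.45 | Shrinkage from 0.45 |
|---|---|---|---|---|---|
| 0.10 | about 23 | 0.429 | 0.434 | 0.440 | 2–5% |
| 0.30 | about 68 | 0.388 | 0.403 | 0.419 | 7–14% |

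The share 14/26 (54%) of deaths falls after the 3-month visit. Under these assumptions those deaths cause no shrinkage, because the carried value already holds the full effect.

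**Step 4. Does the direction hold?** Let eB be the true 6-month effect in bereaved caregivers. The carried values give this group an effect of (6/26) × e6 + (14/26) × 0.45, which is 0.242, 0.294 or 0.346 for the three values of e6. Carry-forward understates the overall effect if eB is above that figure and overstates it if eB is below. The documents give no information on eB.

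**The case against.** The strongest reply is that IV.F is the analysis plan and carries nothing forward. The sentence in IV.E may be a loose remark about the deceased patient's FACT-BMT and about dropouts in general. IV.C schedules caregivers at every visit with no stop at the patient's death, and a caregiver who answers at 3 or 6 months has supplied the last valid measure. This stands in part. A reader might infer that the plan discards measurable distress and scores every bereaved caregiver from a pre-death visit at both 3 and 6 months. The documents do not support that: IV.E is contradicted by IV.F, no rule ends caregiver assessment, and later deaths touch only the 6-month value. What remains is a real contradiction and a real silence.

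A reader might also infer that some 68 caregivers, or most of the planned losses, are affected. The 70% survival has no horizon, and the prior trial's description of dropout does not name death. Section III also mentions families moving out of the area. The 30% case is therefore an upper illustration.

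It is also tempting to say that missing the distress of bereavement biases the comparison. A rise that is equal in both arms cancels from the fPER–TAU difference, so that does not follow without a difference between arms.

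Finally, an estimand limited to the time while the patient is alive is defensible. That is a choice the plan may make, but it has to make it openly.

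**Conclusion.** The concern holds as an unresolved conflict with a gap behind it. IV.E and IV.F prescribe incompatible handling of missing values, and neither defines follow-up or scoring of the primary caregiver outcome after the patient dies. Under either rule, a bereaved caregiver who is not assessed contributes no post-death distress to Aim 3, although it could be collected.

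The numerical effect of carry-forward is modest: 2–5% shrinkage of a 0.45 SD effect at 10% deaths and 7–14% at 30%. This rests on evenly spread deaths, no other losses, and an effect that persists after bereavement. If the effect is smaller in bereaved caregivers, the bias could go either way. The main issue is what the Aim 3 result describes when it is reported as intent to treat. It should be corrected, but it does not undermine the design.

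**What to change.** - In IV.E, delete the carry-forward sentence (at minimum for caregiver outcomes after the patient's death), so that the likelihood mixed model in IV.F is the single primary method.
- State that caregivers stay in follow-up after the patient's death and are offered PSS, CES-D and STAI at the remaining scheduled visits, with freedom to decline.
- In IV.F, state that these observed values enter the Aim 3 model.
- Prespecify one sensitivity analysis that uses caregiver data only up to the patient's death.
- Report the number of bereaved caregivers by arm and visit.

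The cost is a short amendment and one additional model run, with no new visits or instruments. Some bereaved caregivers will decline, the invitation needs sensitive wording approved by the IRB, and the composite will become somewhat more variable.

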For hypotheses addressing group differences for patients and separately for caregivers, outcomes will be evaluated with the same design: 2 groups (**fPER**, TAU) at 2 clinics (CBCI, UCH) over 4 times (prior to transplant, 6 wks., 3 mo., 6 mo.). Mixed models will specify group, clinic, time, and their interactions as fixed effects and subject as a random effect, where subject is assumed independently normally distributed with mean 0 and variance independent of the random errors. The primary caregiver model of composite distress will include caregiver age as a covariate because it related to caregiver distress in our prior study¹¹; secondarily, we will investigate inclusion of patient FACT-BMT as a covariate. The primary patient model of FACT-BMT will include no covariates, but secondarily will explore inclusion of caregiver distress as a covariate.

Aim 4: Assess biomarkers of allostatic load in patients prior to transplant and caregivers during the transplant process using novel biomarkers. Patient's hair cortisol will predict their QOL and distress at the beginning of the transplant process. fPER will be associated with reduced allostatic load in caregivers who receive fPER compared to those receiving TAU.

Linear mixed models will similarly be used to evaluate group differences in these biomarkers separately in patients and caregivers. Caregiver age and patient FACT-BMT will be evaluated for inclusion in caregiver models. Caregiver composite distress score will be evaluated for inclusion as a covariate in patient models.

Subject sample size and power analysis. Our prior trial demonstrated medium effect sizes (0.39-0.45) for PEPRR in caregivers. We believe the proposed modifications in **fPER** will likely increase its effect for caregivers. However, the effect of **fPER** on

Table 2. Minimum detectable effect sizes with specified sample size and power

Sample Size Per Group	80% Power	85% Power	90% Power	95% Power
112 Dyads	0.19	0.20	0.22	0.24
74 Dyads	0.23	0.25	0.27	0.30
62 Dyads	0.25	0.27	0.29	0.32

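### Section IV.E carries the last value forward after death or dropout, section IV.F uses likelihood without imputation, and nothing says which rule governs

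*Combined protocol and SAP*

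**What the plan says.** Section IV.E (Potential Scientific Problems) raises the death of patients and the loss of participants, and answers: "we use intent to treat design with the last valid measure carried forward". The next sentence reads: "Subject dropouts will be considered to occur completely at random unless otherwise indicated".

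Section IV.F, under its paragraph on missing data and attrition, says: "The analytic approach proposed uses maximum likelihood techniques that can include participants with incomplete data without need for imputation". Its stated condition is that "group comparisons will not be biased as long as missing data is ignorable". The same paragraph plans a check that loss is reasonably balanced between groups, a sensitivity analysis if one proves necessary (no method named), and a separate completers analysis. The model is a linear mixed model with group, clinic, time and their interactions as fixed effects and subject as a random effect, over four visits.

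The power section allows for "estimated losses to follow-up of 34% at 3 mo., and 45% at 6 mo", taken from the prior caregiver trial. It calls its estimates conservative because fPER "has been specifically modified to reduce attrition", and adds that "mixed model analyses that include all subjects (even those with only a single observation) have been shown to provide the greatest power".

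IV.F never mentions carry-forward and IV.E never mentions likelihood.

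**The concern.** Carry-forward fills the empty cells before any model is fitted; the likelihood analysis leaves them empty. They are different estimators and can give different answers for FACT-BMT and for caregiver distress. IV.E is written as the method in use, not as a fallback or a sensitivity analysis. An analyst could therefore cite either section, and the choice could be made after the data are seen.

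The stake is bias in the late comparisons. Section IV.D expects quality of life to fall during hospitalisation and possibly for as long as a year, so a pre-transplant score is a poor stand-in for a six-month one. Two fPER sessions fall between months 4 and 6, so an effect still growing at 6 months is plausible. fPER was also designed to improve retention, so unequal loss between arms is foreseeable. Because IV.E gives death as a reason for its rule, followed literally it would assign quality-of-life scores to patients who have died.

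**Working it through.** **1. The plan's own figures.** With 112 per group and losses of 34% and 45%, 112 × 0.66 = 73.9 and 112 × 0.55 = 61.6. These are the 74 and 62 dyads in the minimum-detectable-effect table. The power table is thus built on participants still observed, which fits IV.F rather than IV.E.

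**2. Values filled if IV.E is followed.** Baseline precedes assignment, so each participant should have a value to carry.
- 3 months: 225 × 0.34 = 76.5, about 77. The preliminary-studies section reports 101 of 148 caregivers reaching three months; on that rate 225 × 47/148 = 71.5, about 71.
- 6 months: 225 × 0.45 = 101.25, about 101. Cross-check: 225 − 2 × 62 = 101.

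These counts are per outcome. Applying a caregiver-trial rate to patients is an assumption.

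**3. Values carried past death.** Section I gives 70% survival without a time frame, so the number is unknown. If 10%, 20% or 30% died by 6 months (assumed), it would be about 23, 45 or 68 of 225. These deaths would be part of the overall loss, not added to it.

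**4. Dilution of a growing effect.** Assume the effect grows linearly from transplant and 85% are retained at 6 weeks. The last observed visit is then baseline, 6 weeks, 3 months or 6 months with probability 0.15, 0.19, 0.11, 0.55. The fraction of the six-month effect present at those visits is 0, 0.23 (42/182.6 days), 0.5, 1.
- 6 months: 0.19 × 0.23 + 0.11 × 0.5 + 0.55 = 0.649. With 80% and 90% retained at 6 weeks: 0.637 and 0.660.
- 3 months (fractions 0, 0.46, 1, 1): 0.19 × 0.46 + 0.66 = 0.747; range 0.724 to 0.770.

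**5. Unequal loss, no true effect.** Assume 10 points more loss in TAU and trajectories in SD units at the four visits. The contrast is fPER minus TAU at 6 months.
- Fall that persists (0, −0.5, −0.5, −0.5), extra loss before 6 weeks: an extra 10% of TAU carry 0 instead of −0.5, giving −0.10 × 0.5 = −0.05 SD.
- Fall that recovers (0, −0.8, −0.5, −0.2), extra loss after 6 weeks: an extra 10% of TAU carry −0.8 instead of −0.2, giving +0.10 × 0.6 = +0.06 SD.

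Simulation (112 per arm, within-subject correlation 0.5 and 0.7, single-visit t test) agreed: about −0.05 SD with type I error 6.5-6.7%, and +0.06 SD with 7.0-7.7%. A flat trajectory gives no bias.

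**6. Equal loss, no true effect.** The estimate is unbiased. A single-visit t test is near nominal (4.5-5.4%), with reported SE 0.133-0.138 against empirical SD 0.130-0.139. The planned model is different. A random intercept imposes one common correlation between visits, while carry-forward makes it uneven. With true correlation 0.5 and the probabilities in step 4:
- baseline with any later visit: 0.15 + 0.85 × 0.5 = 0.575 (three pairs);
- 6 weeks with 3 or 6 months: 0.34 + 0.66 × 0.5 = 0.670 (two pairs);
- 3 with 6 months: 0.45 + 0.55 × 0.5 = 0.725.

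The average is (3 × 0.575 + 2 × 0.670 + 0.725)/6 = 0.632. For the baseline-to-6-month change the model SE is therefore about √[(1 − 0.632)/(1 − 0.575)] = 0.93 of the true one. The nominal 1.96 cut-off acts as about 1.82, which rejects in about 7%. Simulation of a random-intercept group-by-time model (clinic omitted) gave 6-8%, with the model SE about 4-10% too small.

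**The case against.** The strongest reply is that IV.F settles the matter. It is the dedicated analysis plan, it addresses attrition by name, it specifies the model and software, and the power section relies on that model. For hair samples too, section IV.D says the statistical approach accommodates missing values. On this view the IV.E sentence is a leftover and only wording is at issue. Most of this stands: likelihood is the better-supported reading. But it is an inference. No text gives IV.F precedence or demotes carry-forward, and IV.F does not discuss death separately.

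Three further objections stand in full.
- IV.F already plans a dropout-balance check, a conditional sensitivity analysis and a completers analysis, so imbalance would probably be noticed.
- IV.E does not mention FACT-BMT. It should not be read as a dedicated rule for that outcome after death; IV.F's rule for incomplete data covers every outcome and every cause of loss.
- Missing completely at random is a special case of ignorable and IV.E hedges it. The two assumptions differ in strength but do not contradict each other. The stronger one sits poorly with the prior trial, where dropouts were linked to patient or caregiver factors, and likelihood does not need it.

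A reader might also infer that carry-forward always distorts the type I error, or that its smaller SE is always false. Step 6 supports neither: with equal loss, the single-visit comparison is sound and only the change contrast in the random-intercept model is affected.

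**Conclusion.** The contradiction is real in the current text and should be fixed. IV.E and IV.F cannot both be the primary handling of the same outcome, and nothing ranks them.

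The consequences are conditional on IV.E being followed. The filled counts (about 71-77 at 3 months, 101 at 6 months, per outcome) rest on planning losses that the plan itself calls conservative. The dilution to 64-66% rests on assumed linear growth and assumed six-week retention. The 0.05-0.06 SD spurious difference rests on an assumed imbalance and assumed trajectories, and is small. The number of values carried past death cannot be determined from the documents.

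A reader might infer that the trial will impute 45% of its six-month data, or that its primary result is biased. The documents do not support that: if IV.F governs, as the weight of the text suggests, none of the carry-forward effects arises.

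**What to change.** - In IV.E, delete the carry-forward clause or label it a sensitivity analysis only.
- State once that the IV.F likelihood mixed model, on observed data under missing at random, is the primary handling for FACT-BMT and caregiver distress.
- State that scores are not carried forward past death.
- Replace the completely-at-random sentence with IV.F's ignorable (missing at random) assumption, which is weaker and sufficient for likelihood.
- Report deaths by arm next to the dropout check already planned.
- Optional: name a non-ignorable sensitivity analysis, such as a delta adjustment.

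The cost is a few sentences. Design, sample size, data collection and the IV.F analysis do not change. The likelihood SE at 6 months is larger than carry-forward would report (about 0.155-0.167 SD against 0.133-0.138 SD, on an assumed within-subject correlation of 0.5-0.7). That is a difference only relative to carry-forward, not a loss against the IV.F plan.
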